#### 4.3.1 Study Treatment Formulation and Packaging

#### 4.3.1.1 Satralizumab and Placebo

IMP will be supplied by the Sponsor as prefilled syringe (PFS) assembled with a plunger rod, needle safety device (NSD), and extended finger flange (EFF) filled with 1.0 mL of solution for SC injection corresponding to 120 mg satralizumab. Satralizumab placebo PFS is identical in composition to satralizumab PFS, but does not contain the satralizumab active ingredient. It will be identical in appearance and packaging to satralizumab. A PFS (assembled with an NSD/EFF) filled with 0.5 mL of solution, corresponding to 60 mg satralizumab, will be used in the OLE period (after the second OLE dose) once it becomes available at the study site.

For information on the formulation and handling of satralizumab, see the pharmacy manual.

# 4.3.1.2 Background Therapy Oral Corticosteroids

For information on the formulation and packaging of OCSs, see the local prescribing information for OCSs.

#### Immunosuppressive Therapy

For information on the formulation and packaging of azathioprine, mycophenolate mofetil, cyclosporine A, tacrolimus, see the local prescribing information for the respective treatment.

#### Acetylcholinesterase Inhibitors

For information on the formulation and packaging of AChEI (pyridostigmine, neostigmine, ambenonium), see the local prescribing information.

# 4.3.2 Study Treatment Dosage, Administration, and Compliance

The treatment regimens are summarized in Section 3.1.

Details on treatment administration (e.g., dose and timing) should be noted on the Study Drug Administration electronic Case Report Form (eCRF). Cases of accidental

overdose, medication error, drug abuse, or drug misuse, along with any associated adverse events, should be reported as described in Section 5.3.5.12.

Guidelines for treatment interruption or discontinuation for patients who experience adverse events are provided in Section 5.1.4.1.

#### 4.3.2.1 Satralizumab and Placebo

Patients will receive satralizumab or placebo at Weeks 0, 2, 4 (loading doses) and maintenance doses Q4W thereafter during the DB period. Patients will receive the second and the third loading dose (administered at Weeks 2 and 4) within a  $\pm$  3-day window for both dosing visits and all subsequent doses within a  $\pm$  7-day window for each dosing visit. The minimal dosing interval between two loading doses is 8 days. It should be noted that the second loading dose and the Week 2 assessments should coincide and occur 14 ( $\pm$ 3) days after Study Day 1.

Study drug will be administered by SC injection in the abdominal or femoral region by the investigator or designated person after all other study-related procedures have been performed at a site visit. For the first 5 doses of study drug in the DB and OLE periods, all patients should be observed for the signs and symptoms of hypersensitivity reactions at the study site for at least 1 hour after administration of study treatment.

In case of disease exacerbation that requires rescue therapy, study drug administration will be continued as scheduled, concurrently with rescue therapy, unless the investigator considers it necessary to discontinue study treatment. Patients who receive PE as rescue therapy will receive loading doses of study drug as soon as possible post-PE.

The dose of study treatment will be determined on the basis of body weight. Patients with a body weight ≤ 100 kg will receive 120 mg SC satralizumab or the matching volume of placebo. Patients with a body weight > 100 kg will receive 180 mg SC satralizumab or the matching volume of placebo, given as two injections (one 1-mL PFS, and one additional 0.5-mL injection).

An interim PK analysis was included to confirm that the achieved exposures are within the target range (see Section 6.11.2). Based on the results of this analysis and pre-specified criteria, the dosing regimen could be modified from 120 mg to 180 mg and from 180 mg to 240 mg for patients  $\leq$  100 kg and > 100 kg, respectively, if needed to achieve target concentrations. For further details on the interim analysis, see Section 6.11.2.

For preparation and administration of the 180-mg or 240-mg doses of study drug (in case of dose modification), please refer to the pharmacy manual.

In the OLE period, all patients can receive open-label treatment with satralizumab, as determined on the basis of body weight, as described above. *Adult and adolescent* patients who receive active treatment during the DB period (Group A) will continue to

receive OLE satralizumab subcutaneously Q4W, with a dose of placebo administered at Week 2 of the OLE period in order to maintain blinding to DB treatment assignment. Adult and adolescent patients who receive placebo treatment during the DB period (Group B) will be administered loading doses of satralizumab subcutaneously at Weeks 0, 2, 4, and maintenance doses Q4W thereafter of the OLE period. After Week 24 of the OLE period and in accordance with local regulations, administration of satralizumab outside of the study site (e.g., mobile nursing by a qualified HCP or home treatment [self-administration or administration by a trained caregiver]) may be allowed on scheduled study drug administration days if no on-site assessments are scheduled for that dosing date (see Appendix 2). The investigator will assess if it is appropriate for a given patient to receive study drug by self-administration or administration by a caregiver outside of the study site. If administration outside the study site is appropriate, patients will be required to give written informed consent to participate in mobile nursing visits or home treatment. Patients and their caregivers will be provided with emergency contact information by the site.

Adolescent patients enrolled directly in the OLE period will receive satralizumab treatment at Weeks 0, 2, and 4 (loading doses) and maintenance doses Q4W thereafter. Patients will receive the second and the third loading dose (administered at Weeks 2 and 4) within a  $\pm 3$ -day window for both dosing visits and all subsequent doses within a  $\pm 7$ -day window for each dosing visit. The minimal dosing interval between two loading doses is 8 days. It should be noted that the second loading dose and the Week 2 assessments should coincide and occur 14 ( $\pm 3$ ) days after Study Day 1.

If eligible for and willing to participate in self-administration, patients and their caregivers will be trained how to administer study drug. After the patient or caregiver signs the Informed Consent for Optional Home Treatment, training of the patient or caregiver can begin from the Week 16 OLE visit and should continue until the patient or caregiver has demonstrated competence in administering the injection of the study drug correctly. The assessment to determine the patient's or caregiver's competence in performing the injection needs to be made by the Principal Investigator (or delegate) and should be documented in the patient's medical records. After the patient or the patient's caregiver has demonstrated competence in giving the injection correctly, SC injections may be administered by the patient or the patient's caregiver at home. Patients should be followed up by the study site personnel through phone calls around the scheduled study drug administration dates to monitor compliance, concomitant medications, and adverse events. If a patient is unable or does not wish to administer study drug at home, clinic staff will continue to administer injections to the patient at the study site.

Patients and their caregivers will be instructed in how to recognize any signs and symptoms of hypersensitivity reaction and to identify when to seek emergency medical care in case of an extreme reaction. Patients will record details of their home -administered study drug injections in a diary. Site personnel will monitor the study medication records from the diary at the in-clinic visits. An HCP who is trained on

study drug preparation, storage and administration should perform the preparation and SC administration of any dose that is not in a form of PFS.

Refer to the pharmacy manual for detailed instructions on drug storage, and administration.

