All female patients of childbearing potential (including those who have had a tubal ligation) will have a serum pregnancy test done centrally at the screening visit. During the study, serum or urine pregnancy tests will be performed at the study site at subsequent visits. For adolescent patients at the time of informed consent, urine  $\beta$ -human chorionic gonadotropin will be recommended during the study except screening in order to reduce the blood volume taken. If a urine pregnancy test is positive, it must be confirmed by a serum pregnancy test.

A female patient is considered to be of childbearing potential if she is postmenarcheal, has not reached a postmenopausal state ( $\geq$  12 continuous months of amenorrhea with no identified cause other than menopause), and has not undergone surgical sterilization (removal of ovaries and/or uterus). The definition of childbearing potential may be adapted for alignment with local guidelines or requirements.

The following samples will be sent to the Sponsor or a designee for analysis:

- PK/PD assessments: serum samples for satralizumab concentration, IL-6, and sIL-6R
- Immunogenicity assessments: serum sample for ADA analysis
- Serum samples for determination of autoantibodies at screening, e.g., anti-AChR, anti-MuSK, and anti-LRP4
- Serum, plasma, blood, and peripheral blood mononuclear cells (PBMCs) samples for exploratory research on biomarkers potentially related to disease, drug, or clinical response and biomarker assay development

Exploratory biomarker research may include, but will not be limited to, the following:

- gMG-associated autoantibodies during the DB and OLE periods (e.g., anti-AChR, anti-MuSK, and anti-LRP4)
- Biomarkers associated with inflammation and T- and B-cell function (e.g., IL-17 and B-cell subsets)
- Live-cell assays in PBMCs, e.g., T- and B-cell activation and proliferation

Research may involve extraction of DNA or RNA; analysis of mutations, single nucleotide polymorphisms, and other genomic variants; and genomic profiling through

٠

<sup>4 For sites in the Netherlands and Germany, the central laboratory autoantibody tests at screening to confirm gMG diagnosis are not required.

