Appendix 2:Schedule of Activities: Schedule of Activities: Open-Label Extension Period (cont.)

	Screening a		F	From \	Veek (	0 to W	eek 2	4			After\	Week 24		US Visit	DD Visit b	RLD Visit 1,2,3°	EOT Visit d	SFU/ EOS Visit e
Week	−4 to −1	O f, g	2	4	8	12	16	20	24	Q4W h	Q12W	Q24W	Q48W					
Window in days	NA	NA	±3	±3	±7	±7	±7	±7	±7	±7	±7	±7	±7				±7	±7
Vital signs °	x	Х	Х	Х	Х	Х	Х	Х	Х		Х	Х	Х	Х	Χ	Х	Х	Х
12-Lead ECG p	x	х				х			х			x	х	х		χ l	х	х
Hematology q,r	х	Х	Х	Х	Х	Х	Х	Х	Х		Х	Х	Х	Х	χs	Х	х	Х
Chemistry t, r	х	Х	Х	Х	Х	Х	Х	Х	Х		Х	Х	Х	Х	x s	Х	Х	Х
Fibrinogen, INR r	x	х	х	х	х	Х	х	Х	х		х	х	х	х		х	х	х
Cortisol u						Х			Х		Х	Х	Х		Х		Х	Х
Low-dose ACTH stimulation test u						х			х		х	х	х		х		х	х
Pregnancy test v	х	х	х	х	х	х	х	х	х	х	х	х	х	х		х	х	х
Urinalysis w	х	Х	Х	Х	Х	Х	Х	Х	Х		Х	Х	Х	Х		Х	Х	Х
TBNK r	х	Х				Х			Х				Х	Х		Х	х	Х
TB screening x,y	х																	
Quantitative Igs r, y, z	х	х				Х			х				х			x 	х	х
C-SSRS		Х	Х	Х	Х	Х	Х	Х	Х		Х	Х	Х	Х		Х	Х	Х

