## Appendix 2:Schedule of Activities: Schedule of Activities: Open-Label Extension Period (cont.)

- a Applicable only to adolescent patients who first enter the study in the OLE period because screening would not have been completed previously. Visit is not specified by the protocol.
- b In the event that the study drug is not administered within the scheduled visit window and is subsequently administered outside the visit window. The minimum dosing interval should be 14 days.
- c RLDs 1 and 2 are needed for drug interruption for a duration between 8 to 12 weeks. RLDs 1, 2, and 3 are needed for a drug interruption longer than 12 weeks, inclusive.
- d An EOT visit will be performed for all patients who permanently discontinue treatment during the OLE period and who continue treatment with satralizumab outside of this study. At this visit a complete set of assessments will be conducted. If the EOT visit coincides with a scheduled visit, the EOT visit should be completed instead of the scheduled visit.
- e Adult patients will be asked to complete a SFU visit 12 weeks after the final dose of satralizumab. Adolescent patients will be asked to complete SFU visits 12 weeks and 24 weeks after the final dose of satralizumab. Patients who decide to continue treatment with satralizumab outside of this study will have to complete the EOT visit, but they will not have to complete the SFU nor the EOS visit.
- f For adult and adolescent patients who complete the DB period, Week 0 visit of the OLE period coincides with the final visit of the DB period. The assessments performed at Week 24 (final week) of the DB period will be used as the active treatment baseline for the patients who receive placebo during the DB period and as the OLE baseline for patients who receive satralizumab during the DB period. Duplicate assessments should be avoided.
- § For adolescent patients who do not complete the DB period and transition to the OLE period, the assessments performed at the visit at which they receive the first active treatment will be used as the active treatment baseline.
- h In accordance with local regulations, administration of satralizumab outside of the study site (home treatment) is allowed. Patients should be followed up by study site personnel through phone calls around the scheduled study drug administration dates to monitor compliance, concomitant medications, and adverse events.

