## Appendix 2:Schedule of Activities: Schedule of Activities: Open-Label Extension Period (cont.)

- n Applicable only for RLD Visits 2 and 3.
- o Includes body temperature, pulse rate, and systolic and diastolic blood pressure while the patient is in a seated position. Vital signs are measured just before dosing and 15 (±5) minutes and 60 (±5) minutes after dosing for the first 5 OLE doses in case of study drug injection visit. Blood pressure and pulse measurements should be preceded by at least 5 minutes of rest for the participant in a quiet setting without distractions.
- p ECG should be performed prior to blood draws.
- q Hematology includes hemoglobin, hematocrit, RBC, WBC (absolute and differential: neutrophils, eosinophils, basophils, monocytes, lymphocytes, and other cells), quantitative platelet count.
- All clinical laboratory, PK, PD, ADA, and biomarker samples should be obtained pre-dose at indicated visits. Samples should be taken in the morning if possible, and approximately at the same time across visits.
- s If study drug was not administered on schedule because of a safety issue with laboratory abnormality, then the relevant laboratory parameter should be tested at the DD Visit.
- t Chemistry includes albumin, total protein, total bilirubin, ALP, AST, ALT, GGT, LDH, total cholesterol, LDL cholesterol, HDL cholesterol, triglycerides, ferritin, BUN, creatinine, sodium, Cl, K, Ca, P, complements (CH50, C3, C4), lipase, CRP, serum CK, and uric acid.
- u For patients on the corticosteroid taper with symptoms of AS early morning cortisol has to be measured. If morning cortisol is normal, but patient has symptoms of AS, perform low-dose ACTH stimulation test to confirm AS diagnosis.
- v Urine pregnancy tests will be performed at specified visits. If a urine pregnancy test is positive, the patient will not receive the scheduled dose, and a confirmatory serum pregnancy test will be performed. Urine β–hCG (sensitivity of at least 25 mU/mL) will be performed locally. *All female adolescent patients of childbearing potential who enter directly in the OLE will have a serum pregnancy test at screening.*

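### Open-label extension, women of childbearing potential: no pregnancy test at delayed-dosing visits, and no stated way to confirm a negative test before a home injection (minor)

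*Protocol*

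**What the plan says.** **Delayed dosing.** The Appendix 2 row "Pregnancy test" is marked in every column except the delayed-dosing (DD) visit, where study drug is marked. In Appendix 1 the same row is marked at the DD visit and does not carry footnote p, which limits a test to delays caused by a laboratory abnormality. Protocol Section 4.3.2.2 expects the assessments of the scheduled visit normally to have been done already, and lets the investigator add tests at the delayed visit.

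**Home dosing.** Section 4.3.2.1 states that after OLE Week 24 dosing outside the site "may be allowed on scheduled study drug administration days if no on-site assessments are scheduled for that dosing date (see Appendix 2". Footnote h, on the 4-weekly (Q4W) column of Appendix 2, states that "administration of satralizumab outside of the study site (home treatment) is allowed", with no exception for women of childbearing potential. That column marks four rows: study drug, pregnancy test, concomitant medications and adverse events. Footnote v makes the test dose-blocking: "If a urine pregnancy test is positive, the patient will not receive the scheduled dose". On location, Section 4.5.6 says: "During the study, serum or urine pregnancy tests will be performed at the study site at subsequent visits". Patients dosed at home are followed "through phone calls around the scheduled study drug administration dates to monitor compliance, concomitant medications, and adverse events", and the injection diary is reviewed afterwards: "Site personnel will monitor the study medication records from the diary at the in-clinic visits".

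**The concern.** Pregnancy requires permanent discontinuation of study treatment (Section 4.6.1), and the pre-dose test is the schedule's means of finding it before a dose is given. The elimination half-life is about 30 days (Section 4.4.2.1), so a dose given in early pregnancy cannot be quickly reversed.

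At a delayed OLE visit, a site that follows Appendix 2 exactly gives a dose with no test at that visit. For home dosing, one site may refuse it on a Q4W date because a test is due there, while another allows it and has no written procedure for obtaining the result first. The stake is consistent safety practice for a subgroup of OLE patients. It is not the estimation of any treatment effect.

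**Working it through.** **1. Is the blank DD cell just part of a lighter open-label visit?** Four rows marked in the DD column of Appendix 1 are blank in Appendix 2:

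| Row | Condition in Appendix 1 |
|---|---|
| Height | adolescents only |
| Fibrinogen/INR | footnote p (only if relevant to the delay) |
| Urinalysis | footnote p |
| Pregnancy test | no such condition |

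Three of the four were already restricted. The pregnancy test was not, so a lighter visit explains its absence less well.

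**2. Age of the last result at a delayed maintenance dose.** Inputs: visit window ±7 days (Appendix 2); minimum maintenance interval 14 days (Section 4.3.2.2); nominal interval 28 days; test done on the nominal date, day 0.

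- Earliest delayed dose: 7 + 1 = day 8.
- Latest, with the next dose on its nominal date: 28 − 14 = day 14.
- Latest, with the next dose at the end of its window: 35 − 14 = day 21. However, the next visit's window opens at 28 − 7 = day 21. Under Table 7 a dose falling in that window is recorded with all assessments of the next scheduled visit, which include a test. The last day without a scheduled test is therefore day 20.

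The result is thus 8 to 14 days old, up to 20. If the scheduled visit was missed altogether, the last scheduled test was 28 days earlier on nominal dates: 28 + 8 = 36 to 28 + 14 = 42 days, up to 28 + 20 = 48.

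**3. What the home-dosing texts imply on each reading of Section 4.5.6.**

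- *Test done on site.* It is then an on-site assessment, and the condition in Section 4.3.2.1 bars home dosing for these women on every Q4W date. Footnote h does not say so.
- *Test done locally rather than centrally.* Home dosing is open. The test is still due, because Section 4.5 requires all scheduled activities, and a positive result still blocks the dose. No supplied text says who does the test or how the result reaches the site.

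Of the four Q4W rows, the calls ("to monitor compliance, concomitant medications, and adverse events") cover three. The pregnancy test is the one left out. The calls are also timed around the dosing date, not before it. Section 4.5 says the schedule will specify what a mobile nurse may do, but the Appendix 2 text as supplied assigns the nurse nothing, and self-injection involves no nurse.

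**4. Ceiling on doses exposed to gap (2).** OLE duration is taken as 2 to 3.5 years (Section 3.3: 2.5 to 4 years in total, less about half a year double-blind), that is, to Week 104 or Week 182. Q12W visits are counted from Week 24.

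- To Week 104: doses at Weeks 28, 32, …, 104 = (104 − 28)/4 + 1 = 20. Q12W dates are Weeks 36 to 96 = (96 − 36)/12 + 1 = 6. Q4W-only: 20 − 6 = 14 (70%).
- To Week 182 (last dose Week 180): (180 − 28)/4 + 1 = 39. Q12W dates: (180 − 36)/12 + 1 = 13. Q4W-only: 39 − 13 = 26 (67%).

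The documents give neither the number of these women nor the share of their doses given at home, so the exposed count per woman lies anywhere from 0 to 14 of 20 (or 0 to 26 of 39).

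**The case against.** The strongest reply is that the dose gate is already written. The test is scheduled every 4 weeks, a positive result blocks the dose, and Section 4.5 makes dosing depend on acceptable local laboratory values. A site dosing at home without a result would be departing from the protocol. This stands, so it would be wrong to infer that the plan permits untested home dosing on about 70% of doses. That figure describes only a site acting on footnote h alone, for a woman who doses at home on every eligible date.

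A reader might also infer that Section 4.5.6 firmly places the test on site and so contradicts footnote h. Context favours the other reading: the test is listed among samples for the site's local laboratory, the sentence follows one about central testing at screening, and footnote v says urine tests are performed locally. Even on the on-site reading, footnote h could be taken as a general permission limited by Section 4.3.2.1, and the investigator decides suitability patient by patient. What remains is an ambiguity that sites can resolve differently.

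Nor can one say that no confirming step exists anywhere. The home-treatment consent form, training material, and pharmacy and laboratory manuals were not supplied and may contain it.

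On delayed dosing, a result 8 to 20 days old is fresher than the 4-week interval the schedule accepts, and the investigator may add a test. Both points stand. They do not cover a missed scheduled visit, nor explain why Appendix 1 tests unconditionally and Appendix 2 does not.

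**Conclusion.** A minor safety inconsistency in two parts, held with medium confidence.

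The DD-cell gap is plain on the face of the two schedules. Its usual effect is a result 8 to 14 days old (at most 20) at dosing, and no current result if the scheduled visit was missed. The 20-day limit assumes the test was done on its nominal date and that Table 7 is followed.

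The home-dosing gap is narrower: the test is required, but its location is ambiguous and confirmation of a negative result before a self- or caregiver injection is not described in the supplied documents. Its frequency cannot be estimated; the Q4W-only counts are a ceiling only.

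The consequence is small. Contraception (Section 4.1.1), the duty to report pregnancy (Section 5.4.3.1) and 12-weekly on-site tests remain, and Section 5.4.3.2 reports no harmful reproductive effects in nonclinical studies, although it says this about partner pregnancies. No efficacy analysis is affected.

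**What to change.** 1. Mark the pregnancy test in the DD column of Appendix 2, as in Appendix 1. Cost: one schedule cell and a urine test at those visits.
2. In footnote h, cross-refer to footnote v and to the on-site condition in Section 4.3.2.1. State that an off-site dose in a woman of childbearing potential requires a negative urine test, confirmed with the site before injection; otherwise the dose is given on site. Align Section 4.5.6 so that it says whether a home or mobile-nurse test is acceptable. Cost: wording, urine kits, and a follow-up call timed before the injection.

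If the home-treatment consent form or manuals already contain the step, a cross-reference to them would meet most of item 2.
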